Exercise Interventions. After completing V2, we will randomize the subjects to one of three 16-week interventions: (i) RE, (ii) REALPA breaks in ST, or (iii) RE+AE (**Figure 3**). The RE+AE group serves as the standard of care. The RE group will complete supervised RE (2 x/wk). The REALPA breaks in ST group will complete a supervised RE (2 x/wk) and regular unsupervised LPA breaks in ST (5 d/wk, 6x10 min breaks/d at 2 METS (~30-40% VO_2 peak), ~500 kcal/wk above resting metabolism). The RE+AE group will complete supervised RE (2 x/wk) and calorically matched moderate intensity AE (3 d/wk, 50 min/session at 4 METS (~60-75% VO_2 peak), ~500 kcal/week above resting metabolism). The RE component for all 3 groups will consist of 3 sets of 10-12 repetitions to failure for a total of 8 exercises targeting the large muscle groups (**Table 2**). The AE component for the RE+AE group will consist of treadmill walking at ~4 METs for 50 min

(Table 2). The RE and AE sessions will take place in LSU School of Kinesiology's Exercise Training Facility under direct supervision (Drs. [name], [name], and [name] with the assistance of trained graduate students). All supervised exercise sessions will include a 5 minute warm-up and cool-down on either a bike or treadmill. We will provide subjects flexibility on the days per week that they can complete their exercise sessions. Note: The start of the exercise intervention will be at least 5 days post V2 to allow for adequate recovery from the muscle biopsy, but no more than 6 weeks after V2. Up to 2 weeks may be added to a subjects exercise intervention, to allow for potential make-up of missed exercise sessions and to provide flexibility for scheduling study visits.

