[name] (LSU) and [name] (PBRC). We will screen all data for distributional properties (mean, median, range) and departures from normality prior to substantive analyses. To test the main effects of time, treatment, and their interaction on the primary outcomes, we will use mixed-effects two-way Analysis of Variance (ANOVA) models ($\alpha=0.05$). The models will include parameters to estimate the main effects of time (pre- and post-training) and treatment (RE, REALPA breaks in ST, RE+AE) on the dependent variables. We will use *Fisher's Least Significant Differences test* to examine within and between group mean differences ($\alpha=0.05$). We will test all models for the main effect of sex. If the main effect of sex is significant, we will perform additional exploratory analyses stratified by sex. Other covariates that may be included in the models include race, change in body weight, and baseline SPPB scores. We will also compare adherence rates across the study groups.

Sample Size, Power Analysis and Randomization. We will use the data collected in this **pilot study** to estimate effect sizes for the primary and secondary outcomes, which we will use to inform our power analyses for a follow-up R01 application designed to test the efficacy of our novel exercise intervention on skeletal muscle and cardiometabolic health in sedentary older adults. We will use a fixed sample size of 12 subjects per group, because increasing the sample size above 12 (i.e., 12 to 15) has diminishing benefit in estimations effect sizes and 95% confidence intervals often referred to as the “rule of 12”.^{39, 40} Thus, we will recruit up to 15 subjects per group to account for a 20% attrition rate. The NIH’s Clinical and Translational Science Awards Biostatistics, Epidemiology, and Research Design (BERD) units recommend 12 subjects per group for estimating effect sizes and 95% confidence intervals.³⁹ Following baseline testing, we will randomize the study subjects to one of the three interventions using a randomized, permuted, block design stratified by sex and race.

PROVISIONS TO MONITOR THE DATA TO ENSURE THE SAFETY OF SUBJECTS

This Human Subjects Research meets the definition of a Clinical Trial. This study does not involve major risk to subjects. Efforts to minimize the potential risks of the assessment methods and outcome variables include frequent monitoring by the investigators to assure that no volunteer suffers any adverse effects from participating in the research.

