Retention Strategies. Retention will be a challenge in the proposed studies, as it is in all clinical trials. Our proposed study provides a variety of benefits in an effort to maximize the number of subjects who complete all follow-up visits. These benefits include the interventions and medical monitoring. Essential aspects of maximizing participation and promoting retention are: 1) carefully screening and assessing barriers to adherence and retention prior to randomization; 2) carefully monitoring adherence problems (which often predict retention problems), trying to identify these problems early before subjects refuse further study contact; and 3) applying specific strategies to address these problems. Some strategies include providing social and emotional support, flexibility in scheduling exercise training session and flexibility in scheduling study visits.

Randomization. After completing both pre-training visit 1 and 2, study subjects will be randomized to one of three 12 week intervention groups i) RE alone, ii) REALPA breaks in sedentary time, or iii) RE+AE. We will prepare randomization scheme based on a permuted block design stratified by sex and race.

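### Randomisation follows V2 but training may start up to 6 weeks after V2, so subjects may know their arm well before any exercise; allocating just before the first session would reduce arm-related losses in that gap

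*Combined protocol and SAP*

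**What the plan says.** Three places time the randomisation, and none gives a day or a maximum interval.

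- Exercise Interventions (Screening and Study Visits): "After completing V2, we will randomize the subjects to one of three 16-week interventions".
- Sample Size, Power Analysis and Randomization: "Following baseline testing, we will randomize the study subjects to one of the three interventions".
- Randomization (Risks to Human Subjects): "After completing both pre-training visit 1 and 2, study subjects will be randomized to one of three 12 week intervention groups". The 12 weeks here conflicts with the 16 weeks elsewhere and must be reconciled.

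The start of training is timed from V2, not from randomisation: "at least 5 days post V2 to allow for adequate recovery from the muscle biopsy, but no more than 6 weeks after V2". The same section adds "Up to 2 weeks may be added to a subjects exercise intervention".

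On numbers: "We will use a fixed sample size of 12 subjects per group", and "Thus, we will recruit up to 15 subjects per group to account for a 20% attrition rate". The Study Population section gives the totals: up to 45 randomised, 36 completing.

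The plan does not say when the subject learns the arm and describes no blinding of subjects. It defines no analysis set, missing-data rule or handling of subjects who leave before the first session.

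**The concern.** Per week, the arms ask for two supervised sessions (RE), two supervised sessions plus 5 x 6 = 30 unsupervised bouts (REALPA), or 2 + 3 = 5 supervised sessions (RE+AE). A subject cannot fail to notice which was drawn. Under the Compensation section the exercise visits are unpaid, and the next paid visit after V2 is V3, in the last week of training. A subject disappointed with the arm therefore has little reason to wait for the start date.

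Two things could follow.

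- **Withdrawal that depends on arm.** It would count after randomisation although no training had been received. With 15 per arm and 12 needed, each arm can lose three.
- **Changed activity that depends on arm.** The primary baseline measures (isokinetic strength, DXA, fasting blood, mixed meal test) are complete by V1, and no repeat before training is planned. The REALPA breaks are unsupervised light walking, which a subject who knows the arm could begin early. The baseline monitors are handed back at V1, and later monitoring is described for the intervention period, so the gap may go unrecorded.

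Before allocation, neither behaviour could depend on the arm.

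**Working it through.** **1. The plan's own figure.** Inputs: 12 completers per group and 20% attrition (Sample Size section).

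12 / (1 − 0.20) = 15 per group; 3 x 15 = 45; 45 x 0.80 = 36. This reproduces the plan. Allowed losses: 45 − 36 = 9 in total, 15 − 12 = 3 per arm. Since up to 45 are randomised and 36 complete, the 20% counts losses after randomisation.

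**2. Length of the gap.** If allocation is made on completing V2, the gap to first exercise is 5 days to 6 weeks. If it is made later, which the word *after* permits, the gap is shorter and could be nearly nil. Six weeks is therefore a maximum. At that maximum the gap is 6 / (6 + 16) = 27% of the time from allocation to the end of training.

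**3. Expected losses in the gap.** The documents give no rate. Assumption: a constant dropout hazard, with the planned 20% spread over gap plus training. Then

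loss before first session = 1 − 0.8^(gap / (gap + training)).

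With 16 weeks of training:

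| Gap | Share of time | Loss before start | Of 45 | Of the 9 allowed |
|---|---|---|---|---|
| 5 days (0.71 wk) | 0.043 | 0.9% | 0.4 | 5% |
| 2 weeks | 0.111 | 2.4% | 1.1 | 12% |
| 4 weeks | 0.200 | 4.4% | 2.0 | 22% |
| 6 weeks | 0.273 | 5.9% | 2.7 | 30% |

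With the optional two extra weeks (18 weeks of training) the range is 0.4 to 2.4 subjects. With the 12 weeks stated in the Randomization paragraph it is 0.6 to 3.2.

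**4. Effect on the target.** If allocation moved to the first session, attrition after randomisation would be 1 − 0.8^(16 / (gap + 16)): 19.2% for a 5-day gap, 15.0% for a 6-week gap. The target would be 12 / (1 − 0.192) = 14.9 or 12 / (1 − 0.150) = 14.1. Both round up to 15, as they do with 18 weeks. Only 12 weeks of training with a full 6-week gap gives 13.9, which rounds up to 14.

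**The case against.** The strongest reply is that the timing is unspecified rather than wrong. A team that randomises at the first session already complies with the text. A reader might infer that the plan imposes a six-week interval between allocation and training; it does not, because the window runs from V2. That stands, and it makes six weeks an upper bound. But the only stated trigger is completion of V2 or of baseline testing, and nothing stops a team from acting on it at once.

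Other parts of the reply:

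- **Size.** A reader might suppose a loss of 5–10% in the gap. That would be 2.25 to 4.5 of 45, or 25–50% of the nine allowed, but no passage supports such a rate. Losses could cluster once the arm is known, yet the documents hold no data on this.
- **Replacement and outcomes.** It is tempting to say that a subject lost before allocation can be replaced, and that one lost in the gap has no outcome. Neither is established. The Overall Approach section applies the ceiling of 45 to people completing screening and the pre-training visits, so a subject lost after V2 may already occupy a place. Nothing bars post-training visits for a subject who never trained. A mixed model can in principle use baseline-only records, although the plan does not say that it will.
- **Existing safeguards.** The Retention Strategies paragraph plans to look for barriers before randomisation, and scheduling is flexible. Both help; neither removes the gap.
- **Preparation.** The arms need different arrangements. This is a real cost, but a limited one: the two weekly resistance sessions are common to all arms and can be booked before allocation.

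**Conclusion.** The point holds as a cheap improvement to the design. As written, the plan lets unblinded subjects know an arm of very different burden for up to six weeks before exposure. It allows three losses per arm and has no rule for subjects who leave early. Under a constant hazard the expected loss in the gap is about 0.4 to 2.7 of 45; the upper figure requires every subject to be allocated at V2 and to wait the full six weeks.

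This concerns possible bias and clarity. A reader might infer a sample-size error, but 15 per group stands for 16 or 18 weeks of training. A reader might also infer that late allocation removes arm-related dropout. It reduces only losses before the start; a subject can still leave at or after the first session, and that calls for an analysis rule covering everyone randomised. Nor does it shorten the wait; it only prevents behaviour before allocation from depending on the arm. The primary baseline values are not in question, since they precede randomisation.

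**What to change.** Use one statement of timing in all three places:

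- Allocate and disclose the arm at the last contact before the first training session, after all baseline measures. The Screening Visit, Part II text lets the 1-RM be deferred to the first week of training; any deferred 1-RM should be completed before allocation.
- Leave the 5-day to 6-week window unchanged.
- Record the dates of allocation, disclosure and first session, and report losses between allocation and first session by arm.

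The cost is wording and the timing of the allocation step. Arm-specific arrangements (the aerobic sessions, the reminders for activity breaks) are made at shorter notice. Sample size and stratification are untouched. If subjects have already been randomised, the reporting by arm is still worth doing, because the pilot is meant to inform the planning of a follow-up trial.

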The LPA breaks in ST will consist of walking at ~2 METS for 6x10 min bouts, which will be completed throughout the day, with ~1 bout per hour. Alternative 2 MET mobility-based activities may also be provided using the Compendium of Physical Activities to promote adherence. We may use text/email messaging to send reminders, the "Stand Up! The Work Break Timer" (Apple/Android App) to promote adherence to the LPA breaks in ST protocol. We may also use the CentrePoint Cloud-Based Data Capture and Management Platform to send reminders to study participants. We will initially send these reminders on the days in which the subjects do not report for their RE sessions, the frequency of these reminders may be increased or decreased based on adherence. To reduce the risk of injury and muscle soreness, we will progressively increase the intensity and volume of the exercise prescriptions to the targeted training intensities over the first month of the intervention. Prior to each training session, we will assess resting blood pressures and heart rates. We will not allow subjects to exercise if they have a resting diastolic blood pressure > 100 mm Hg, resting systolic blood pressure > 180 mm Hg, or resting heart rate > 100 beats per min. We will also assess heart rates using heart rate monitors (e.g., Polar or Zephyr Bioharness) and ratings of perceived exertion (RPE, Borg 6-20) throughout the supervised exercise sessions. We will also measure the subjects' weight once per week during one of their scheduled exercise visits.

	Mon	Tue	Wed	Thu	Fri
A. Resistance Exercise (RE)		
 • Leg Press • Leg Extension • Leg Curls • Chest Press • Lat Pulldowns • Shoulder Press • Triceps Extension • Biceps Curls 
3 Sets 10-12 Reps to Failure
		
 • Leg Press • Leg Extension • Leg Curls • Chest Press • Lat Pulldowns • Shoulder Press • Triceps Extension • Biceps Curls 
3 Sets 10-12 Reps to Failure
	
B. LPA Breaks in Sedentary Time*	6x10 min bouts at 2 METS	6x10 min bouts at 2 METS	6x10 min bouts at 2 METS	6x10 min bouts at 2 METS	6x10 min bouts at 2 METS
C. Aerobic Exercise	1 x50 min bouts at 4 METS		1 x50 min bouts at 4 METS		1 x50 min bouts at 4 METS

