Exercise Interventions. The RE group will complete 16 weeks of supervised RE training (2 x/wk). The REALPA breaks in ST group will complete 16 weeks of supervised RE training (2 x/wk) and regular unsupervised LPA breaks in sedentary time (5 d/wk, 6x10 min breaks per day at 2 METS (~30-40% VO₂ peak), ~500 kcal/wk above resting metabolism). The RE+AE group will complete 16 weeks of RE (2 x/wk) and calorically matched moderate intensity AE (3 d/wk, 50 min/session at 4 METS (~60-75% VO₂ peak), ~500 kcal/week above resting metabolism). The RE component for all three groups will consist of 3 sets of 10-12 repetitions to failure for a total of 8 exercises targeting the large muscle groups (See Research Strategy for Details). The RE and AE sessions will take place in LSU School of Kinesiology's Exercise Training Facility under direct supervision (Drs. [name], [name], and [name] with the assistance of trained undergraduate and graduate students). Over the first month of the intervention, we will be progressively increase the intensity and volume of the exercise prescriptions to the targeted training intensities and volumes to reduce the risk of injury and muscle soreness. Prior to each RE and/or AE training session, we will assess resting blood pressures, heart rates, and clinical symptoms. We will not allow subjects to exercise if they have an absolute contraindication to exercise (see Potential Risks Section

Below). We will also assess heart rates using heart rate monitors (e.g., Polar or Zephyr Bioharness) and ratings of perceived exertion (RPE, Borg 6-20) throughout the supervised exercise sessions.

b. Sources of Materials.

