18. Exercise Interventions. The risks associated with the three exercise training interventions are those commonly associated with moderate to vigorous physical activity in older adults. The proposed exercise interventions are unlikely to cause major problems. We have conducted numerous exercise training studies and have never had a serious adverse event. There is the possibility of adverse events ranging from minor musculoskeletal problems to, in very rare cases, cardiovascular events. Occasionally study subjects experience minor orthopedic problems, but most are self-correcting with rest and standard first aid. These orthopedic injuries will be minimized by gradually progressing subjects to their prescribed dose at the start of the study and, if necessary, alternating exercise sessions between cycle ergometers and treadmills. Exercise supervisors are trained in first aid and basic CPR. All RE and AE sessions will be supervised by trained personnel in the LSU's School of Kinesiology's Exercise Training Facility. The LSU School of Kinesiology's Exercise Training Facility is well equipped with emergency response equipment including automatic defibrillator. Although some study subjects will be at moderately elevated risk for CVD, they will receive a thorough health screen including a physical examination by a study physician and a maximal exercise test. According to the available data on adverse events resulting from the types of exercise proposed here, risk should be low in this study. Fatal events during exercise are extremely rare.¹⁶ All resistance exercise (RE) and aerobic exercise (AE) training sessions will be supervised by a trained exercise specialist. The risk associated with the low intensity physical activity breaks in sedentary time are unlikely to cause any major problems. Prior to each exercise session, resting blood pressure, heart rate, and clinical symptoms will be assessed. Subjects will not be allowed to commence their exercise session if they have an absolute contraindication exercise,¹⁶ which includes

- a. Unstable Angina
- b. Resting systolic blood pressure > 200 mm Hg or diastolic blood pressure > 110 mm Hg
- c. Uncontrolled sinus tachycardia (resting HR >120 beats/min)

19. MMTT. There is a possibility of pain, bruising, or infection at the site of the needle insertion for the IV line. Trained personnel minimize this risk. The drink may make cause nausea, vomiting, abdominal bloating, or a headache.

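### The protocol gives two conflicting sets of blood pressure and heart rate limits for holding a training session, and does not say which governs

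*Combined protocol and SAP*

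**What the plan says.** Three places in the combined protocol and SAP deal with clearing a subject before a session.

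- **Screening and Study Visits, Exercise Interventions.** "Prior to each training session, we will assess resting blood pressures and heart rates". Then: "We will not allow subjects to exercise if they have a resting diastolic blood pressure > 100 mm Hg". The same sentence goes on to bar exercise for systolic pressure above 180 mm Hg or heart rate above 100 beats/min. This text does not mention symptoms.
- **Risks to Human Subjects, Exercise Interventions.** "Prior to each RE and/or AE training session, we will assess resting blood pressures, heart rates, and clinical symptoms". It gives no numbers and continues: "We will not allow subjects to exercise if they have an absolute contraindication to exercise (see Potential Risks Section", so the reader is sent on to Potential Risks.
- **Potential Risks, item 18.** "Prior to each exercise session, resting blood pressure, heart rate, and clinical symptoms will be assessed". Then: "Subjects will not be allowed to commence their exercise session if they have an absolute contraindication exercise". The list that follows has three entries: unstable angina; resting systolic above 200 or diastolic above 110 mm Hg; and uncontrolled sinus tachycardia with resting heart rate above 120 beats/min.

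The label also appears at screening. Exclusion criterion 20, in both the Study Population section and the human-subjects section, excludes for an absolute contraindication to exercise. Its values are diastolic above 100, systolic above 180 and heart rate above 100. It cites reference 16, which item 18 of Potential Risks also cites for its own, higher values.

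**The concern.** A session-hold limit should have one value, because staff apply it on the day without time to reconcile sections. Here one term, *absolute contraindication*, carries two sets of numbers under one citation, and the human-subjects section makes that term the criterion for holding a session. Its cross-reference leads to the looser set.

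At stake is subject safety. Subjects are 65 to 80 years old and train with resistance sets to failure. Item 18 says that some will be at moderately elevated cardiovascular risk. A supervisor using the human-subjects section and Potential Risks could start a session at a reading that the Exercise Interventions text bars and that criterion 20 would have excluded at screening. A supervisor using only the Exercise Interventions text would apply the stricter numbers but would not be told there to check symptoms.

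**Working it through.** There is no sample size or error rate to reproduce. The check sets the two lists side by side and applies each to the same readings.

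**Inputs and differences**

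| Measure | Exercise Interventions (Screening and Study Visits) | Potential Risks, item 18 | Difference |
|---|---|---|---|
| Resting systolic, mm Hg | > 180 | > 200 | 200 − 180 = 20 |
| Resting diastolic, mm Hg | > 100 | > 110 | 110 − 100 = 10 |
| Resting heart rate, beats/min | > 100 | > 120 | 120 − 100 = 20 |
| Symptoms | not mentioned | assessed; unstable angina listed | – |

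Both apply at the same moment, before each session, so they are not rules for different occasions.

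**Applying each list to example readings** (systolic/diastolic, heart rate)

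| Reading | Exercise Interventions | Potential Risks, item 18 |
|---|---|---|
| 180/100, 100 | not barred | no listed limit met |
| 190/95, 80 | barred (systolic) | no listed limit met |
| 170/105, 80 | barred (diastolic) | no listed limit met |
| 150/85, 110 | barred (heart rate) | no listed limit met |
| 200/110, 120 | barred (all three) | no listed limit met |
| 201/111, 121 | barred (all three) | barred (both pressures and heart rate) |

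The disputed band is therefore systolic above 180 up to 200, diastolic above 100 up to 110, or heart rate above 100 up to 120, with no item 18 limit exceeded and no other reason to hold.

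**Direction.** Each item 18 limit lies above its counterpart (200 > 180, 110 > 100, 120 > 100). Any reading that exceeds an item 18 pressure or heart rate limit therefore also exceeds one in the Exercise Interventions text. On these measures the stricter text contains the looser one.

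**Precedence.** Nothing in the three sections, or in criterion 20, says which set governs a session. Criterion 20 matches the stricter values, but it is a screening rule. As values for holding a session, the count is one section against one.

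**The case against.** The strongest reply is that the two texts can be reconciled. Both are prohibitions. Item 18 introduces its list as inclusive, not exhaustive, and nowhere says that a subject in the band may exercise. The bar in the Exercise Interventions text is unconditional, and that section is the operating procedure, whereas item 18 sits in a description of risks. Staff who follow the procedure satisfy every blood pressure and heart rate limit in the document. The symptom check is required before each session in two places, so silence in the third does not cancel it. Other safeguards remain: a history of cardiovascular disease is excluded, subjects have a physical examination, resting ECG and exercise test, and resistance and aerobic sessions are directly supervised.

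All of this stands, and it limits the point. It does not remove it. Reconciling the texts depends on having read both and noticed the difference, and the human-subjects section directs its reader only to the looser list.

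Three stronger readings are tempting but unsupported:

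- *Potential Risks allows exercise in the band.* It does not say so; it only fails to list those readings.
- *The hold rule is scattered, so no single section contains it.* The Exercise Interventions text is a complete blood pressure and heart rate rule, and item 18 stands alone with symptoms included. The problem is two self-contained rules that disagree.
- *Reference 16 shows which set is right.* The reference is not available here, and the protocol cites it for both.

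**Conclusion.** The inconsistency is real and should be fixed. Two sets of session-hold limits differ by 20 mm Hg systolic, 10 mm Hg diastolic and 20 beats/min, with no stated order of precedence. The cross-reference in the human-subjects section leads to the looser set. Confidence is high for the mismatch itself, which follows from the text alone.

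The possible harm rests on an assumption: that some staff would work from the human-subjects section and Potential Risks without the Exercise Interventions text. The documents do not show that this happens. They also give no rate for readings in the disputed band, so the number of affected sessions cannot be estimated and none is offered. A reader might infer an effect on power, type I error, adherence or adverse event rates; nothing in the documents supports one.

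**What to change.** 1. In Potential Risks, item 18, replace the blood pressure and heart rate limits with resting diastolic above 100 mm Hg, systolic above 180 mm Hg or heart rate above 100 beats/min, worded as the study's own session-hold limits. Keep unstable angina and the symptom check.
2. In the Exercise Interventions text under Screening and Study Visits, add the clinical-symptom check.
3. Have the Exercise Interventions text in the human-subjects section and item 18 of Potential Risks both refer to that one rule.
4. Ask the medical investigator to confirm the rule and to check whether the attribution to reference 16 is correct where it is used, including exclusion criterion 20.

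The cost is a wording amendment and a staff briefing; no new data are needed. The downside is possibly some additional held sessions, at an unknown rate and only where staff now apply the looser list. The protocol already allows flexibility in training days and up to two added weeks for make-up sessions and visit scheduling, so held sessions can be rescheduled within that allowance.
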